2.3.1 QUALITATIVE INTERVIEW PART

In total, n = 12 qualitative interviews will be conducted with four patients per study group to explore the patient perspectives and preferences regarding IAD prevention. This number is based on the recommendations for doing qualitative research in feasibility studies for RCTs [22]. To consider possible sex related differences, two male and two female participants will be included per group. To be eligible, patients need to have a MMSE score of 24 or higher. A separate consent is required for participation in the interview. Interviews will be transcribed verbatim and qualitative content analyzes conducted.

2.3.2 CRITERIA FOR DISCONTINUING

Nursing home/hospital level:

- (1) If the institution no longer wants to participate,
- (2) Any circumstance that makes it impossible or irresponsible to continue study at the respective institution

Resident/patient level:

- (1) If a participant or its legal representative withdraws its consent,
- (2) Adverse events (AEs) that, in the judgment of study personnel, interfere with further participation in the trial,
- (3) Serious adverse events (SEAs),
- (4) Incidents that, in the judgment of study personnel, interfere with further trial participation,
- (5) Serious incidents,
- (6) The occurrence of a medical condition which is incompatible with continued trial participation.

These include, for example:

- a. Mycotic or bacterial inflammation, or other skin conditions in the study area that require topical (drug) treatment of the skin area with other products,
 - b. The development of a category II, III, IV pressure ulcer, or an unstageable pressure ulcer, or a suspected deep tissue injury (DTI)
- (7) If participants are permanently transferred outside the study site
 - (8) In the intervention groups: missing application of study products for more than 72 hours
 - (9) More than three missing study visits

An "adverse event" or "serious adverse event" is in accordance with the definitions of Regulation (EU) 2017/745 (MDR) as defined in Article 2(57) and (58). An "incident" or "serious incident" is in accordance with the definitions of Regulation (EU) 2017/745 (MDR) as defined in Article 2(64) and (65).

For the whole trial:

- (1) If the ethics committee withdraws the ethics approval
- (2) If after 8 months of recruitment less than $n = 60$ participants have been included
- (3) The CTAB unanimously decides after 8 months that study continuation is not suitable to answer the research questions.

2.4 EDUCATION

2.4.1 TRAININGS

Training courses of 60 minutes will be conducted by the research team to educate the nurses and involved care givers in study-relevant procedures. This includes the demonstration of the study related procedures by the research team as well as an exercise for the caregivers on the correct use of the products. The trainings will be conducted before the study starts in the participating institutions. The number of trainings held initially is based on the number of staff to be trained, to ensure that a sufficient number of the involved caregivers have received the training. At regular intervals of about three months, follow-up training sessions are conducted by the study staff in the institutions to check and refresh knowledge about the study and its procedures and to involve new caregivers.

2.4.2 MATERIALS

In addition to the trainings, written/illustrated instructions, explaining the correct use of materials and describing the protocol-compliant conduct of study related procedures, will be provided to give nurses the possibility to review and refresh relevant information at any time. It is planned that these materials will be made available in print as well as digital form. For this purpose, booklets and presentations will be prepared. Furthermore, DIN-A1 posters will be placed in the participating wards to increase the awareness of the study and to provide a quick overview of the related procedures at any time.

In addition, color-coded laminated cards will be placed in the participants' rooms, preferably close to their incontinence materials. The color of the card reflects the assignment to the study

group and contains a minimum of information about the correct conduct of procedures in the respective study group. These cards will serve as a reminder for caregivers and help to avoid confusion regarding group assignment. Measures to prevent accidental unblinding of the outcome assessor are taken (see section 3.3 , page 31).

2.5 STRATEGIES TO IMPROVE COMPLIANCE AND ADHERENCE TO THE STUDY PROTOCOL

Prior to inclusion of an institution, interested institutions are visited by the study coordinators. During this visit, the background and procedures of the study are explained and the importance of adhering to the study protocol and the provision of sufficient nurses and other caregivers is emphasized. If the study coordinators are confident that the institution meets the requirements, has the impression that the study-related procedures can be performed correctly and the institution demonstrates willingness to participate, the institution is eligible for inclusion in the study. Prior to participation, institutions sign a written informed consent form. After inclusion, ongoing communication with nursing homes and hospitals will be maintained throughout the study to prevent premature loss of participating institutions.

During the study visits in the participating institutions, the study personnel will review diaries completed by the caregivers at least every second day. The high frequency of visits will increase the caregivers' attention of the study and provide the opportunity for regular communication between the caregivers and the study staff. The study staff can immediately identify missing data and inconsistencies in the diaries and discuss and resolve them directly with the caregivers. This timely and prompt approach will significantly contribute to data quality and completeness. Likewise, the caregiver has the opportunity to clarify open questions with the study staff promptly at any time.

2.6 CONCOMITANT CARE AND INTERVENTIONS

[figure not shown]
According to the pragmatic nature of this study there are no restrictions regarding concomitant care or treatments as long as they do not interfere with the conduct of the study.

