2.3 INTERVENTIONS

Included participants of all three groups receive a standardized skin cleansing regime consisting of cleansing of the skin with water and the addition of a mild cleansing product. Cleansing is done using disposable washing mitts. To remove possible residual stool from the skin, an additional skin oil can be used. After subsequent gentle drying of the skin, elastic disposable breathable incontinence pants are put on. This is considered as 'standard incontinence care'. In order to ensure the greatest possible standardization and uniformity, the same predefined products and procedures are used for all participants. The required products for the participants will be provided by the investigators and are listed in Table 1.

After baseline visits, included residents/patients will be randomly assigned on Day 0 to one of the following three study arms:

- **Study arm 1 (Experimental intervention I):** Standard incontinence care with additional daily topical application of a film-forming leave-on skin protectant (ESENTA™ Hautschutz Spray) that builds a protective layer on the surface of the skin
- **Study arm 2 (Experimental intervention II):** Standard incontinence care with additional daily topical application of a lipophilic leave-on skin protectant (Hydrophobes Basisgel DAC) that forms a hydrophobic physical barrier on the skin
- **Study arm 3 (Control group):** Standard incontinence care alone, no additional intervention in the control group

The interventions are described in detail according to the template for intervention description and replication (TIDieR) checklist [17] in Table 1. The items 10 and 12 do not apply for study protocols and are therefore not listed in the table [17].

Table 1: Description of interventions according to the template for intervention description and replication (TIDieR) [17].

Item	Experimental intervention I	Experimental intervention II	Control group
1. Brief name	Film-forming leave-on skin protectant for IAD prevention	Hydrophobic leave-on skin protectant for IAD prevention	No skin protectant

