4.1 Demography and baseline characteristics

Demographic information (e. g. age, sex, care level), incontinence type according to medical records, medical information (e. g. relevant main medical diagnoses and relevant regular medication) and further care specific data is collected for all participants.

Characteristic	eCRF table	Variable name	Type	Scale	Comment/Analysis
Patient-ID		mnpaid			
Visit Number		mnpvismo			
	mnppid_random				Randomization information (strata)
arm		rd_0050	cat	1-A 2-B 3-C	Blinded (label permuted)
	mnppid_visit				Visit information
Visit performed?		visit_0011	Cat.		
Date of visit		visit_0012	Date		
Reason for no visit		visit_0013	Char.		
Setting		sc_0020	Cat.	1-Nursing home (NH) 2-Geriatric Hospital (GH)	Important: mnppid_visit; not mnppid_screening! =>rename setting_sc_0020
	mnppid_completion				
Date of study termination		sc_0010	Date		For “time under study” Take diff(sc_0010,visit_0012==Day0)
Did the subject complete the study regularly?		sc_0021	cat	1-Yes, completion of end of study visit on Day 14 2-Yes, but before end of study visit on Day 14 0-No	Reasons for 0 might be withdrawal before randomization or screening failure
Reasons for early termination		Sc_0031 to Sc_0038			Consider sc_003x_txt Except for 0031,0032,0037

Characteristic	eCRF table	Variable name	Type	Scale	Comment/Analysis
	mnppid_demo				Demography & Medical Data
A Demography					
Age		dm_0020	Cont.	years	Mean (sd)
Sex		dm_0030	cat	1-male 2-female	n (%)
Body height		dm_0041	Cont.	cm	Mean (sd)
Body weight		dm_0051	Cont.	kg	Mean (sd)
BMI		dm_0060	cont	Score	Mean (sd)
Care level		dm_0070	cat	0-none 1-1 2-2 3-3 4-4 5-5 -1-Unknown	n (%)
Smoking status		dm_0080	cat	1-Smoker 2-Non-Smoker -1-Unknown	n (%)
Skin type		dm_0090	cat	1-I 2-II 3-III 4-IV 5-V 6-VI	n (%)
B Medical Data					
Relevant medical diagnoses (ICD 11)			multi		Multiple answers possible
None		dm_0101	cat	0-no 1-yes	n (%)
Hypertension		dm_0102	cat	0-no 1-yes	n (%)
Dementia		dm_0103	cat	0-no 1-yes	n (%)
Renal failure		dm_0104	cat	0-no 1-yes	n (%)
Diabetes mellitus		dm_0105	cat	0-no 1-yes	n (%)
Heart arrhythmia		dm_0106	cat	0-no 1-yes	n (%)
Unknown		dm_0107	cat	0-no 1-yes	n (%)
Relevant medications			multi		Multiple answers possible

Characteristic	eCRF table	Variable name	Type	Scale	Comment/Analysis
None		dm_0111	cat	0-no 1-yes	n (%)
Antithrombotics		dm_0112	cat	0-no 1-yes	n (%)
Beta-adrenoreceptor antagonists		dm_0113	cat	0-no 1-yes	n (%)
Diuretics		dm_0114	cat	0-no 1-yes	n (%)

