7.2 Analyses of endpoints

Because of the exploratory nature of the trial and according to methodological guidance for exploratory trials, a distinction between primary and secondary endpoints is not made [23]. Because the main aim is to prevent IAD, IAD incidence is likely to be considered as a primary outcome in a possible subsequent confirmatory trial and is therefore considered as primary efficacy variable.

For all outcomes, total group differences are reported by the corresponding effect size based on the statistical models as outlines below and corresponding 95% confidence intervals. Relevant timepoints will be Day 6 and Day14. Day0 reports will be presented as is.

The relevant blinded group comparisons are: A vs. B; A vs. C; B vs. C.

For cumulative incidence rates of IAD, Kaplan-Meier Curves will be presented with time ranging from inclusion to IAD onset, i.e. the first occurrence of IAD 2A or 2B. Censoring occurs if patients withdraw from the study before the onset of an IAD or if the study is terminated before IAD onset. Mixed effects Cox regression model (shared frailty model) will be carried out for group comparisons of incidence rates. The latter includes group allocation, sex, setting (nursery home, geriatric hospital ward) and time (continuous) as fixed effects and random intercepts for the ward and the patients. The resulting Hazard ratios for IAD will be presented. Potential non-linear time effects will be explored and modelled using fractional polynomials or splines.

Group differences for categorical, dichotomous responses are calculated by estimating group effects from either generalized linear mixed-effects models (binary logistic) - including particular baseline status (maceration, IAD-related itch), group allocation, sex, setting and time as fixed effects and random intercepts per ward and patients - or nonparametric analysis of longitudinal data depending on the distribution of the data. For the Erosion model, no baseline adjustment is considered due to its presence is an exclusion criterion.

List:

- Erosion (no/ yes)
- Maceration (no/ yes)
- IAD related itch (no/ yes) [only measured if IAD present]
- IAD-related pain (no/yes) [only measured if IAD present]

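### Participants who leave because the study skin worsened are censored before the 2A/2B event, and sections 2.6 and 2.3.2 do not settle when another topical product ends participation

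*Combined protocol and SAP*

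**What the plan says.** Protocol 2.6 makes concomitant care conditional: "there are no restrictions regarding concomitant care or treatments as long as they do not interfere with the conduct of the study". It does not define interference and does not mention leave-on products applied to the study skin.

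Protocol 2.3.2 lists the grounds for ending a participant's involvement. Criterion (6) is "The occurrence of a medical condition which is incompatible with continued trial participation", and its first example is "Mycotic or bacterial inflammation, or other skin conditions in the study area that require topical (drug) treatment of the skin area with other products". No arm is named. Criterion (8), by contrast, applies to the product arms only: "In the intervention groups: missing application of study products for more than 72 hours". Section 4.1.1 also lets the blinded skin assessor end participation for an incompatible condition, with the reason recorded.

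Category 1A skin is eligible at entry, while topical treatment of the IAD area is an exclusion criterion (2.2.2). The control arm receives "Standard incontinence care alone, no additional intervention in the control group" (2.3).

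Protocol 4.4 and SAP 2.2 analyse people who discontinue only up to the point of leaving. SAP 7.2 defines onset in the main time-to-event analysis as the first category 2A or 2B, and states: "Censoring occurs if patients withdraw from the study before the onset of an IAD". SAP 4.1 lists "Reasons for early termination" as variables sc_0031 to sc_0038, with accompanying text for most of them.

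**The concern.** There are two linked gaps.

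**An undefined boundary.** Suppose a participant with 1A redness is given a barrier product from outside the trial. The redness may not amount to a condition under criterion (6)a. Section 2.6 does not say whether the product interferes. No analysis rule covers the case, except that use of a wrong product removes the participant from the per-protocol set.

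**Informative censoring.** A participant who develops 1B has clinical infection with the skin still intact. That is not an event in the main analysis, yet it can be a ground for exit under criterion (6)a. The participant then leaves the risk set because the skin that defines the endpoint has got worse. Kaplan-Meier and Cox estimates assume that people censored at a given time have the same later risk as those who stay, given the model covariates. Here that is implausible.

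At stake are the control incidence and the hazard ratios, which the trial exists to supply to a confirmatory trial. A confidence interval does not reveal this kind of error.

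**Working it through.** **Plan's own figures.** There is no effect size, event rate, power or loss rate to reproduce. The plan raises 60 per arm to 70, which corresponds to a loss of 10/70 = 14.3%, since 60/(1 − 1/7) = 70. Totals agree: 3 × 60 = 180 and 3 × 70 = 210. The plan does not say how much of this loss would be skin-related, or how it would split by arm.

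**Passages side by side.** A 1B case can exit under 2.3.2 (6)a, is analysed only to that point (SAP 2.2), and is censored without an event (SAP 7.2). The planned alternatives do not repair this:
- The per-protocol set drops users of a wrong product, which repeats the selection.
- The complete-case analysis (SAP 7) has no data after exit.
- Imputation (SAP 5.1) is planned only if data are missing at random or completely at random; nothing is specified otherwise.
- The any-category analysis (SAP 7.3) covers only people without IAD at baseline.

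**Two-risk model.** All rates are assumptions: 14 days, constant hazards, 30% of participants at 4 times the hazard of the rest, product hazard ratio 0.5 and control incidence 20%. The low-risk hazard λ solves 0.3·exp(−4·14λ) + 0.7·exp(−14λ) = 0.80, so 14λ ≈ 0.1248 (0.182 + 0.618 = 0.800). Halving the hazard gives a product risk of 1 − (0.234 + 0.658) = 10.9% (unrounded 0.1086). The underlying difference is 20.0 − 10.9 = 9.1 points. The ratio of cumulative hazards is ln(0.8914)/ln(0.80) = 0.515.

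High-risk participants then leave at rate ρ = −ln(1 − f)/14, where f runs from 10% to 50% by Day 14, and are censored.

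| Who leaves | Ratio of cumulative hazards | Risk difference, points |
|---|---|---|
| Nobody | 0.515 | 9.1 |
| Controls only | 0.524 to 0.570 | 8.9 to 7.4 |
| Both arms equally | 0.515 to 0.513 | 9.0 to 8.4 |
| Product arm half as often as control | 0.519 to 0.545 | 8.9 to 7.9 |
| Product arm only | 0.507 to 0.464 | 9.3 to 10.2 |
| Controls start another product and stay, at the product hazard | 0.523 to 0.558 | 8.9 to 7.8 |

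Control-only exits cost 9.1 − 8.9 = 0.2 to 9.1 − 7.4 = 1.7 points. The control estimate itself falls from 20% to between 19.7% and 18.3%. At 10% control incidence the difference falls from 4.8 to between 4.6 and 3.8 points; at 30% it falls from 12.9 to between 12.6 and 10.6.

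For scale, the 95% half-width of the risk difference with 60 per arm is 1.96·√(0.20·0.80/60 + 0.109·0.891/60) = 12.8 points.

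**Worst case.** Take 60 per arm, 12 control events (20%) against 10% on product, and m controls removed who were all certain to have the event. The control risk is (12 − m)/(60 − m).
- m = 1: 11/59 = 18.6%, difference 8.6 points
- m = 2: 10/58 = 17.2%, difference 7.2
- m = 3: 9/57 = 15.8%, difference 5.8
- m = 6: 6/54 = 11.1%, difference 1.1, a loss of 8.9 of 10 points

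In mirror image, removing 1, 2 or 3 such people from the product arm gives 20 − 5/59, 20 − 4/58 and 20 − 3/57 (fractions as percentages), that is 11.5, 13.1 and 14.7 points.

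**The case against.** A reader might infer that 2.6 and 2.3.2 (6)a flatly contradict each other. They do not. Section 2.6 is conditional, and (6)a can be read as one instance of interference. Its trigger is a condition that requires treatment, not the act of starting a product. The entry exclusion and the per-protocol rule on wrong products point the same way. What is missing is a definition.

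A reader might also infer that the exits fall on controls, who have no protectant to fall back on, so that the product effect must shrink. Criterion (6)a names no arm, and the documents do not present either protectant as a treatment for infection. The only arm-specific removal rule, criterion (8), acts on the product arms and could push the other way. Nor do the documents show that sites treat like patients differently: the study team conducts the visits, and under 4.1.1 a blinded assessor judges incompatible conditions.

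It can fairly be said that the plan is partly prepared. Termination reasons are recorded and inform the judgement on missingness (SAP 5.1). The full analysis set lists stopping treatment and leaving the study separately. Imputation could absorb some of the problem if its model used the last observed skin category. The trial is also exploratory, and the milder model's shift is small beside the 12.8-point half-width.

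These points limit the size and fix no direction. They do not remove the gap. No section says that skin assessments continue once the regimen stops, the imputation model is not described, and no planned analysis treats a skin-related exit as an outcome.

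**Conclusion.** The point holds as an undefined boundary plus informative censoring of unknown direction. Estimates move towards no effect if skin-related exits are commoner among high-risk controls. The hazard ratio hardly changes if exits are equal, although the control incidence is still understated. The apparent effect grows if high-risk product-arm participants leave more often.

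With the assumed 20% control incidence and control-only exits, the plausible shift is 0.2 to 1.7 points. Near-total loss of a 10-point difference needs six of twelve control events to vanish, with none lost on product; it is a limit, not an expectation. The documents give no exit rate, event rate or risk by arm, so every size here rests on stated assumptions. The change is worth making because it is cheap and protects the quantities that the trial is meant to estimate.

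**What to change.** **For this trial (SAP only).** SAP 3 reports 220 participants recruited (14 + 11 + 195), so changes to conduct come too late. In SAP 7.2:
- Tabulate (6)a exits and all other early terminations by arm and reason, from sc_0031 to sc_0038 and their text. If a reason code reflects criterion (8), it could reveal which label is control, so produce this table after the main models are run.
- Add a sensitivity analysis in which the event is the first of 2A/2B, a skin-related exit, or the start of a non-study topical product in the study area. Read it beside the main analysis.
- Have the unblinded diary reviewer (SAP 4.4.3) supply coded start dates, if the diaries hold them, so that the statistician stays blinded.

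**For the confirmatory protocol.** Reconcile 2.6 with 2.3.2 (6)a so that one definition of interference applies in every arm; the sponsor decides which products it covers. State in 2.3.2 that ending the assigned regimen does not by itself end the scheduled skin assessments to Day 14, unless consent is withdrawn or the participant leaves the site. Include that follow-up in the main analysis.

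**Cost.** One table and one sensitivity analysis now; later, the remaining scheduled visits for a few participants. Protocol Table 1 has nurses record leave-on products, but the SAP lists only counts of product applications, so capture of non-study products may be incomplete and should be checked first.

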2.7 OUTCOMES AND VARIABLES

Because of the exploratory nature of the trial and according to methodological guidance for exploratory trials, a distinction between primary and secondary endpoints is not made [23]. Because the main aim is to prevent IAD, IAD incidence is likely to be considered as a primary outcome in a possible subsequent confirmatory trial.

Table 2: Outcomes and variables per participant

Outcome Name	Device/Measurement instrument/Scale and metric	Time points	Response Options/Categories/ Range
IAD incidence	
 • IAD Classification according to GLOBIAD [24] and distinction between intact and eroded skin according to Proceedings of the Global IAD Expert Panel [10] • Cumulative incidence • IAD Localization according to the following definition: 
 ○ Back: Sacral region going down to the upper thighs, bordered approximately 5 cm below the gluteal fold ○ Front: Navel to upper thigh 	Days 0, 2, 4, 6, 8, 10, 12, 14	
 • Presence of IAD: 
 (1) None; (2) Category 1 A; (3) Category 1 B; (4) Category 2 A; (5) Category 2 B • Localization of IAD: 
 (1) Back (2) Front
Erythema	
 • Rating according to the item 'Redness' of the incontinence-associated dermatitis and its severity (IADS) instrument [25] • 3-Item-Scale (ordinal) 	Days 0, 2, 4, 6, 8, 10, 12, 14	
 • Redness: 
 (1) None; (2) Pink; (3) Red/Bright red

Outcome Name	Device/Measurement instrument/Scale and metric	Time points	Response Options/Categories/ Range
	
 • Mexameter MX18 with MDD 4 (Courage + Khazaka Electronic GmbH) [26] (measurements according to SOP „Mexameter® MX 18“ Version 1.0, 18.05.2022) (see Fehler! Verweisquelle konnte nicht gefunden werden.) • Arbitrary units (AU) from 0 (= no erythema) to 999 (= extreme erythema) • Means of duplicate measurements at the cranial end of the gluteal cleft 	Days 0, 2, 4, 6, 8, 10, 12, 14	
 • Erythema level: 0 - 999 [numeric; AU]
Erosion	
 • Definition of erosion according to the latest International League of Dermatological Societies glossary of cutaneous lesions [27]: “Loss of either a portion of or the entire epidermis” 	Days 0, 2, 4, 6, 8, 10, 12, 14	
 • Presence of Erosion: (1) No; (2) Yes
Maceration	
 • Definition of maceration according to review article [28]: “(…) maceration (...) is the result of prolonged exposure (of the skin) to moisture and causes the skin to soften and breakdown so that the connective fibres can be teased apart and the skin often exhibits a white appearance.” 	Days 0, 2, 4, 6, 8, 10, 12, 14	
 • Presence of Maceration: (0) No; (1) Yes

Outcome Name	Device/Measurement instrument/Scale and metric	Time points	Response Options/Categories/ Range
IAD related pain	
 Numeric rating scale (NRS) from 0 (= no pain) to 10 (= worst possible pain) (see Fehler! Verweisquelle konnte nicht gefunden werden.) for patients/residents without cognitive impairment (according to Mini-Mental-State-Examination (MMSE) [29] with scores of 24 or higher) Means 	Days 0, 2, 4, 6, 8, 10, 12, 14	
 IAD related pain: 0 - 10 [numeric]
	
 Pain Assessment in Advanced Dementia (PAINAD-G) scale [30, 31] (see Fehler! Verweisquelle konnte nicht gefunden werden.) will be used for patients/residents with dementia (according to MMSE [29] scores of < 24; see Fehler! Verweisquelle konnte nicht gefunden werden.) Means 	Days 0, 2, 4, 6, 8, 10, 12, 14	
 IAD related pain: 0 - 10 [numeric]
Patient satisfaction	
 Definition according to [32]. NRS from 0 (= dissatisfied) to 10 (= very satisfied) (see Fehler! Verweisquelle konnte nicht gefunden werden.) for patients/residents with MMSE [29] scores of 24 or higher Means 	Days 0, 2, 4, 6, 8, 10, 12, 14	
 Patient satisfaction: 0 - 10 [numeric]
IAD related Itch	
 Patient reported IAD related itch 	Days 0, 2, 4, 6, 8, 10, 12, 14	
 Presence of IAD related itch (0) No (1) Yes

Outcome Name	Device/Measurement instrument/Scale and metric	Time points	Response Options/Categories/ Range
Safety	
 Local intolerances according to [34] 5-Item-Scale (ordinal) 	Days 0, 2, 4, 6, 8, 10, 12, 14	
 Presence of Local intolerances: 
 (0) None; (1) homogeneous redness with scattered papules; (2) homogeneous redness and homogeneous infiltration (3) homogeneous redness and infiltration with vesicles (4) homogeneous redness and infiltration with coalescing vesicles
	
 Adverse Events (AEs): According to the definition of the EU regulation 2017/745 Medical Device Regulation (MDR) Article 2 (57) Serious Adverse Events (SAEs): According to the definition of the EU regulation 2017/745 MDR Article 2 (58) Incidents: According to the definition of the EU regulation 2017/745 MDR Article 2 (64) Serious incidents: According to the definition of the EU regulation 2017/745 MDR Article 2 (65) 	Day 0, Day 2, Day 4, Day 6, Day 8, Day 10, Day 12, Day 14	
 SAEs according to the definition of the EU regulation 2017/745 MDR Article 2 (58) will be documented on separate reporting forms (see Fehler! Verweisquelle konnte nicht gefunden werden.) Incidents and Serious Incidents according to the definition of the EU regulation 2017/745 MDR Article 2 (64) and (65) will be documented and reported to the Bundesinstitut für Arzneimittel und Medizinprodukte (BfArM)

Outcome Name	Device/Measurement instrument/Scale and metric	Time points	Response Options/Categories/ Range
Feasibility	
 Willingness to participate (proportion of participants from all eligible patients, reasons for non-participation) 		
 Percentage of persons from the eligible population who are willing to participate: xx [%] Reasons for declining participation: 
 Feel too old or too ill to participate Perceive study participation as a burden Do not want additional/ other treatment Do not see benefits in participating Not interested in research Do not want to be randomly assigned to a treatment Not interested (reason not specified) Other [free-text]
Adherence/ compliance to prescribed intervention	
 Number of applied skin care procedures per day according to diary 		
 Percentage of completely/ correctly documented days: xx [%] Number of used products xx [quantity]

